9.8 Protocol specific grading: Injection Site Reactions

Grade 1	Grade 2	Grade 3	Grade 4

Tenderness with or without: Itching Erythema Swelling Ulceration (fluid vesicle or ulcer <10mm)
 
Minimal effect on activities of daily living.
	
Pain with or without: Erythema Swelling Phlebitis Lipodystrophy Oedema Ulceration (blood vesicle or ulcer ≥10mm)
 
Restricts activities of daily living.
	
Severe tissue damage; operative intervention indicated
 
Prevents or severely limits activities of daily living.
	
Life-threatening consequences; urgent intervention indicated

## 10 ASSESSMENT OF EFFICACY

Response will be assessed to measure any potential responses to trial treatment.

Disease will be measured according to the modified Immune-Related Response Criteria (irRC) given in [Appendix 3](#).

### 10.1 Timing and type of tumour assessments

All patients will have been evaluated by radiological (CT, MRI) disease assessment as part of their routine care and prior to trial entry. A pre-treatment, baseline assessment must be performed within 28 days of the planned first vaccination. This can be an assessment performed specifically for the trial or may be an assessment which was performed as per clinical practice which complies with the 28 day timeframe for baseline assessments.

All patients that receive at least one AST-VAC2 vaccination will be further evaluated following their last vaccination by the imaging modality performed at baseline.

Index and non-index lesion(s) should be selected from the pre-treatment scan. Index lesions are measurable ( $\geq 5 \times 5$  mm) and non-index lesions are non-measurable ( $< 5 \times 5$  mm).

At baseline, the sum of products of the two largest perpendicular diameters (SPD) of all index lesion(s) is calculated. At the post-treatment tumour assessment, the SPD of the index lesion(s) and of any new measurable lesions ( $\geq 5 \times 5$  mm) are added together to provide the total tumour burden.

All tumour measurements must be clearly documented on the pre and post treatment scan reports.

Copies of the scans (including those taken pre-trial) must be available for external independent review if requested by the Sponsor.

### 10.2 Tumour response

All patients who meet the eligibility criteria, receive at least one AST-VAC2 vaccination, have a baseline assessment and at least one repeat assessment of measurable disease will be evaluable for response. Response assessment will be performed in accordance with irRC by defining the change in total tumour burden relative to baseline measurements ([Appendix 3](#)). Response categories as per Appendix 3. Should rapid tumour progression occur before the completion of the scheduled six AST-VAC2 vaccinations the patient will be classified as having early progression (EP).

Expert reviewers appointed by the Sponsor may undertake an independent review of the Investigator's assessed objective responses immune response complete response (irCR) and immune response partial response (irPR). Any independent reviewer's assessment will also be documented in the final Clinical Study Report (CSR) along with the original assessment made by the Investigator. The eCRF will reflect the Investigator's opinion.

#### 10.2.1 Recording of response in the eCRF

All pre and post treatment tumour measurements and an applicable overall response category must be recorded in the eCRF.

## 11 PATIENT WITHDRAWAL BEFORE COMPLETION OF TREATMENT SCHEDULE

AST-VAC2 has been classified as an ATIMP therefore extended follow up (up to five years post first vaccination) is applicable for all patients who receive the IMP.

The Investigator must make every reasonable effort to keep each patient on trial for the whole duration of the trial in order to collect long term safety and pharmacodynamic data. However, if the Investigator removes a patient from the trial (prior to completion of the vaccinations) or if the patient declines further participation, final assessments (as per the 'End of Vaccination' visit), should be performed ideally before any subsequent therapeutic intervention. All the results of the evaluations and observations, together with a description of the reasons for withdrawal from the trial, must be recorded in the patient's medical records and in the eCRF.

A patient may stop vaccination due to AEs but would not be withdrawn from the trial and would continue for follow-up of safety, survival and tertiary endpoints unless they withdraw.

The following are justifiable reasons for the Investigator to withdraw a patient from the trial.

- Withdrawal of consent.
- Serious deviation from the trial protocol (including persistent patient attendance failure and persistent non-compliance).
- Sponsor's decision to terminate the trial.
- Withdrawal by the Investigator for clinical reasons not related to AST-VAC2.
- Loss to follow up.

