#### 5.3.2 Dose delays & interruptions

If at the time of the next scheduled vaccination day, one or more adverse events (AEs) (excluding ISRs) related to the AST-VAC2 vaccine (highly probably, probably or possibly related) are still present, have not resolved to Grade  $\leq 1$  and are considered by the Investigator to be clinically significant and a clear contraindication to vaccination, the next vaccination day should be delayed for up to two weeks until the AE(s) have recovered to this level. In case of uncertainty, individual cases should be discussed with the Sponsor. Patients who require a dose interruption of greater than two weeks will be reviewed on a case by case basis to determine whether the patient should be withdrawn from the trial. The Sponsor will confirm whether an extended interruption is acceptable or if the patient should be withdrawn from further trial treatment.

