#### 7.4.3 Two years post first vaccination visit (survival follow up data collection).

All vaccinated patients should be followed up for OS, two years post the first vaccination. Evaluation of new or ongoing AST-VAC2-related AEs should be performed. Any concomitant medications relevant to these AEs should also be recorded. The AE information can be collected via a phone call to the patient. Survival information may be obtained from the patient's medical records.

For survival follow up, sites will be asked to provide the following information if known:

- Date of death or date of last contact if alive.
- Reason for death.
- All post trial anti-cancer treatment for primary disease.
- Date of radiological confirmed relapse(s), if post trial.
- WHO PS at time of relapse.
- Any other medically important information, in the opinion of the investigator.

No further patient trial related visits or assessments are required to collect this survival data. Survival follow up information may cease to be collected based on emerging data showing limited immune response and therefore limited benefit of continuing collection of long term follow up data. This will be discussed and agreed by the Sponsor and CI based on emerging data.

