**7.4.4 Extended follow up (>2 years to 5 years post first vaccination)**

After the 2-year survival follow up has been completed, any patients who are still alive will continue to be followed up every three months by telephone until the end of the trial (unless the patient has died or withdrawn from the trial). If the patient has died, the date of death and cause of death will be recorded. Evaluation of new or ongoing AST-VAC2-related AEs should be performed. Any concomitant medications relevant to these AEs should also be recorded. It is acceptable for there to be flexibility around when these quarterly calls take place but this should be checked with the Sponsor who will document the revised visit accordingly.

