### 9.3.3 Eligible patients

For eligible patients, SAE and AE collection and monitoring will commence at the time the patient gives their written consent to participate in the trial by signing the main trial consent form and will continue until 30 days after the last vaccination (administration of IMP). From this time point until the patient withdraws, dies or completes the trial, new or ongoing AST-VAC2-related AEs will be collected (regardless of whether the patient goes on to other anti-cancer therapies).

Should an Investigator become aware of any AST-VAC2 -related SAEs after the patient has completed the protocol-mandated follow-up period (as specified above), these must also be reported to the Sponsor within the expedited timelines in Section 9.4.

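### Section 11 applies five-year follow-up to every vaccinated patient, yet allows withdrawal from the trial without the patient asking; this ends the year 2 to 5 calls and leaves the rules for earlier follow-up in conflict

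*Protocol*

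**What the plan says.** Section 11 of the protocol opens by stating that, because the product is an ATIMP, "extended follow up (up to five years post first vaccination) is applicable for all patients who receive the IMP". It asks investigators to make every reasonable effort to retain patients. It also expressly keeps one group in follow-up: "A patient may stop vaccination due to AEs but would not be withdrawn from the trial".

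The same section then states: "The following are justifiable reasons for the Investigator to withdraw a patient from the trial". Five reasons follow. Two are patient-driven or unavoidable: withdrawn consent and loss to follow-up. The other three can be applied without the patient asking:

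- serious deviation, including persistent non-attendance;
- the sponsor's decision to terminate;
- "Withdrawal by the Investigator for clinical reasons not related to AST-VAC2", with no definition.

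Other sections depend on whether a patient has been withdrawn:

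- Section 7.4.4 requires calls every three months after year 2, "unless the patient has died or withdrawn from the trial". The calls collect related AEs and the date and cause of death.
- Section 9.3.3 sets the period for collecting related AEs after the 30-day point: "From this time point until the patient withdraws, dies or completes the trial".
- Section 7.4.3 says "All vaccinated patients should be followed up for OS, two years post the first vaccination". It makes no exception for withdrawal and allows medical records as the source.
- Section 5.3.2 says that an interruption of more than two weeks is reviewed "to determine whether the patient should be withdrawn from the trial". Its next sentence speaks only of withdrawal from further treatment. The SAP's paragraph on vaccination delays refers, like the quoted sentence, to withdrawal from the trial.

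**The concern.** AST-VAC2 is a first-in-human product derived from human embryonic stem cells. Section 3.3.3 names autoimmunity and tumorigenicity or ectopic growth among the events that trigger independent review, and Section 13.1 ties the data collected after the two-year cut-off to ATIMP safety reporting. Scheduled long-term contact is how late events of this kind would be found. A rule that lets an investigator or sponsor decision end that contact, while the same section says it applies to every treated patient, gives sites two incompatible instructions.

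Sponsor termination matters most. Section 12 gives toxicity as an example of a cause, and nothing in the protocol says that patients already exposed keep their safety contacts afterwards.

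**Working it through.** The plan gives no figure to reproduce: there is no power calculation, no assumed dropout and no formal analysis. The check sets the passages side by side and then does simple arithmetic for scale.

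**Which withdrawal is meant.** Sections 3.2, 5.4 and 12 refer the reader to Section 11 for withdrawal from the trial. Section 5.4 also refers to Section 11 for further reasons to stop vaccination. One list therefore serves two purposes.

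**What happens to a vaccinated patient withdrawn from the trial by the investigator or sponsor:**

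| Data | Text that stops or closes it | Text that continues it | Result |
|---|---|---|---|
| Calls in years 2 to 5 | 7.4.4 | Opening of Section 11 only | Ends |
| Routine related AEs beyond 30 days after the last vaccination | 9.3.3 | 7.4.1 and 7.4.2 schedule AE evaluations with no withdrawal exception | Ends under 9.3.3, the section that sets the collection period |
| Visits at 3, 6 and 12 months | 9.3.3 for AEs | 5.4 asks patients withdrawn from vaccination or from the trial to keep attending, for immune samples | Conflict |
| Two-year survival | 13.1 counts the patient as finished for the analysis trigger | 7.4.3, all vaccinated patients | Conflict |
| Related SAEs | None | 9.4, if the investigator becomes aware | Passive only |

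**Level of withdrawal in 5.3.2.** For a related AE that interrupts dosing for more than two weeks, one sentence refers to withdrawal from the trial and the next to withdrawal from treatment. Section 11 says that a patient who stops because of AEs stays on trial. The footnote to SAP Table 9 agrees with Section 11; the SAP paragraph on delays does not.

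**Scale.** Inputs: at most eight patients (Section 1.6), five years = 60 months, calls begin after 24 months.

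- Share per patient: 1/8 = 12.5%, and more if fewer are recruited.
- Clearest loss in a patient alive at two years: 60 − 24 = 36 months, or 36/3 = 12 quarterly calls.
- Two-year survival: if k of 8 patients have unknown status, the proportion alive can be placed only within a range k/8 wide. One patient gives 12.5 percentage points; two give 2/8 = 25. SAP Table 15 and Outcome Measure 6 have only alive and deceased, so such a patient has no row.
- Chance of seeing at least one late related event, 1 − (1 − p)^n. The rates p are assumed, since the documents give none:

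| p per patient | 8 followed | 7 followed |
|---|---|---|
| 5% | 33.7% | 30.2% |
| 10% | 57.0% | 52.2% |
| 20% | 83.2% | 79.0% |

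Under these assumptions, losing one patient costs about 3.5 to 4.8 percentage points of detection.

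**The case against.** The strongest reply is that the rest of the protocol protects most patients.

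- Section 5.4 treats progression as a reason to stop vaccination. Section 5.3.2 keeps follow-up going for anyone withdrawn from further treatment unless consent is withdrawn or the sponsor says sampling is not needed.
- Sections 5.5 and 9.3.3 continue collecting related AEs after other anti-cancer therapy, and SAP Section 4.1 keeps such patients evaluable for survival. (Section 9.3.4 and footnote j of the schedule stop follow-up of an existing related AE when other therapy starts; that is a separate inconsistency.)
- The participant flow in SAP Section 7.2 already separates the two levels. Physician decision and sponsor termination appear only as reasons for not completing vaccination. Exits from follow-up are loss to follow-up, withdrawn consent, death and declining a visit.

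Much of this stands, and it rules out a stronger reading. A reader might infer that a patient progressing at Week 4 could be withdrawn for unrelated clinical reasons and lose about 59 of 60 months of follow-up, and that two-year survival would then lose the patients with the worst prognosis. The documents do not support that. Section 11 does not equate those reasons with progression, the provisions above keep such a patient in follow-up, and Section 7.4.3 requires survival status for every vaccinated patient. Counting withdrawn patients in the Section 13.1 trigger sets the timing of the analysis; it does not stop survival being ascertained.

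The reply does not remove the conflict. The 5.3.2 protection covers withdrawal from treatment, not from the trial. The SAP flow is a reporting template that ends at two years. The retention clause in Section 11 is followed directly by permission to remove patients. Nothing covers patients already exposed when the sponsor terminates, beyond a general duty in Section 12 to consider their interests.

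**Conclusion.** The contradiction is real and should be corrected. For a vaccinated patient withdrawn from the trial without having asked, the text ends the year 2 to 5 calls and routine related-AE collection, against Section 11's own statement of scope. For the first 12 months and for two-year survival, the finding is conflicting instructions, not certain loss.

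The size is bounded but not known. Each patient is at least 12.5% of the set, and the clearest loss is up to 36 months of calls in a patient alive at two years. That loss needs a patient to survive two years, in a population eligible with a life expectancy of 12 weeks or more and no other suitable treatment. The documents give no basis for the number of patients affected. The conclusion assumes that withdrawal in Sections 7.4.4 and 9.3.3 includes withdrawal decided by the investigator or sponsor, as the cross-references to Section 11 indicate.

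**What to change.** 1. In Section 11, separate stopping vaccination from ending follow-up data collection. State that safety and survival follow-up of a vaccinated patient ends only on death, withdrawal of consent to follow-up, confirmed loss to follow-up, or completion of five years. This is close to the follow-up exits already in SAP Section 7.2. Section 7.4.3 separately lets the sponsor and chief investigator stop collecting survival data; cite that as an exception or align it.
2. Make Sections 7.4.4, 9.3.3 and 13.1 use the same exits.
3. State whether exposed patients keep their scheduled safety contacts after sponsor termination.
4. Reconcile Sections 5.3.2, 5.4 and 11 and the SAP paragraph on vaccination delays, so that each says which level of withdrawal it means. Which reasons should stop vaccination is a clinical matter for the sponsor and investigators and is not addressed here.
5. Add an unknown-status row to SAP Table 15 and Outcome Measure 6, and say how a patient withdrawn by the investigator or sponsor is classified there.

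The cost is a wording amendment to both documents, plus quarterly calls continuing for the few patients who would otherwise be closed out, possibly including after an early termination.

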## 12 DEFINING THE END OF TRIAL

The 'End of Trial' is defined as the date when all patients have either withdrawn (see [Section 11.0](#)) from the trial or died, or the last patient has completed their final follow-up visit (whichever is the latter). The final follow-up visit is scheduled to take place five years after the patient's first vaccination.

It is the responsibility of the Sponsor to inform the MHRA and the REC within 90 days of the End of the Trial that the trial has closed.

In cases of early termination of the trial (for example, due to toxicity) or a temporary halt by the Sponsor, the Sponsor will notify the MHRA and the REC within 15 days of the decision and a detailed, written explanation for the termination/halt will be given.

Recruitment will cease when:

- The drug is considered too toxic to continue treatment before the required number of patients have been recruited.
- The stated number of treated patients to be recruited has been reached.
- The stated objectives of the trial have been achieved.

Regardless of the reason for termination, all data available for patients at the time of discontinuation of follow-up must be recorded in the eCRF. All reasons for discontinuation of treatment must be documented.

In terminating the trial, Sponsor and the Investigators must ensure that adequate consideration is given to the protection of the patient's interests.

## 13 DATA ANALYSIS AND STATISTICAL CONSIDERATIONS

Further development of the AST-VAC2 program will consider the following factors:

- Demonstration that vaccination administration is feasible with an acceptable safety profile,
- Demonstration of durable immune response as per the trial secondary endpoint,
- Demonstration of an increase in OS.

### 13.1 Interim analysis

An interim analysis will be conducted once all patients administered AST-VAC2 have withdrawn, died or completed their two-year follow-up visit for survival.

Once this condition is met, a data cut-off will be established. All patient visits occurring on or before this date will be analysed and summarised in the clinical study report including safety data to date and assessment of overall survival at two years.

Any data collected after this date will be summarised in a supplemental report produced for the final analysis to satisfy the safety reporting requirements for AST-VAC2 as an ATIMP.

### 13.2 Final analysis

The final analysis will be conducted after one of the following conditions is met:

- The trial is terminated early e.g. due to toxicity
- The End of Trial as defined in [Section 12.0](#) has been reached.

Once one of the conditions is met, a data cut-off date will be established. All patient visits occurring on or before this date will be analysed and summarised in a supplemental report.

### 13.3 Presentation of data

Data will be presented in a descriptive fashion. Variables will be analysed to determine whether the criteria for the trial conduct are met. This will include a description of patients who did not meet all the eligibility criteria, an assessment of protocol deviations, IMP accountability and other data that impact on the general conduct of the trial.

Baseline characteristics will be summarised for all enrolled patients. Patients who died or withdrew before treatment started or did not complete the required safety observations will be described and evaluated separately.

Treatment administration will be described for all cycles. Vaccine administration, modifications or delays and the duration of treatment will be described.

### 13.4 Safety

Safety data will be collected from the date of written consent until patients have completed their required follow up period. Safety variables will be summarised by descriptive statistics. Laboratory variables will be described using the NCI CTCAE Version 4.02 and the protocol specific grading system for ISRs.

Adverse events will be reported as tables of frequency of AEs by body system and by worse severity grade observed. Tables should indicate related and unrelated events.

Deaths reported within 30 days of the last vaccination and SAEs will be described separately.

A safety review committee, consisting of all investigators and representatives of the Sponsor, will review emerging safety data on an ongoing basis, with particular reference to ensuring that patients are able complete the vaccination schedule without AST-VAC2 toxicity-related delays. Should the committee

have significant concerns about toxicity seen during the trial they will have the authority to suspend or terminate the trial and/or make recommendations to the Sponsor to modify vaccination administration.

**13.5 Pharmacodynamics**

The pharmacodynamic analyses to be performed are described below. Reports will undergo a quality control (QC) step prior to finalisation and will be signed by the person responsible for performing the assays and the laboratory quality assurance (QA) manager once final.

Pharmacodynamic biomarker	Analysis plan
HLA status	HLA A*02:01 status to confirm eligibility is a pre-screening assessment and will be performed by Luminex or similar method at a central laboratory. The whole A* allele will be reported during this pre-screening assessment. [Redacted]
hTERT specific T cell ELISPOT analysis	Vaccine induced ELISPOT response in blood will be reported longitudinally for each patient. Analysis as defined by the Sponsor.
[Redacted]	[Redacted]
[Redacted]	[Redacted]
[Redacted]	[Redacted]
[Redacted]	[Redacted]
[Redacted]	[Redacted]
[Redacted]	[Redacted]

**13.6 Tumour response**

Disease assessment will be performed at baseline and following completion of the vaccination schedule for measurement of potential responses to trial treatment. Patients who receive at least one vaccination and have both a baseline and at least one repeat assessment, will be evaluable for response.

Objective responses and the best tumour response achieved by each patient while on trial and overall survival will be described and presented in data listings.

Overall survival data will continue to be collected (at those time points noted in [Section 7.4](#)) for up to two years after the first vaccination for all patients or until all patients have died, according to whichever event occurs first.

